14.4.2. Secondary Efficacy Endpoints

- 1) Proportion of patients with gallstone formation within 3, 6, 9, and 12 months after gastrectomy. The frequency and proportion of subjects with gallstone formation at each time point and the corresponding 95% confidence interval are provided for each treatment group. And the difference in the gallstone onset rate between each treatment group of DWJ1319 and the placebo is analyzed using a logistic regression model with the lymph node resection range and the type of gastrectomy as covariates.
- 2) Proportion of patients with gallstone formation within 3, 6, 9 months after gastrectomy according to the assessment by an external investigator

The frequency and proportion of subjects with gallstone formation at each time point and the corresponding 95% confidence interval are provided for each treatment group according to the

Confidential Page 34 of 51

assessment of outside researchers. And the difference in the gallstone onset rate between each treatment group of DWJ1319 and the placebo is analyzed using a logistic regression model with the lymph node resection range and the type of gastrectomy as covariates.

- 3) Proportion of patients with biliary sludge within 3, 6, 9, 12 months after gastrectomy. The frequency and proportion of subjects with the formation of biliary sludge at each time point and the corresponding 95% confidence interval are provided for each treatment group. And the difference in the biliary sludge onset rate between each treatment group of DWJ1319 and the placebo is analyzed using a logistic regression model with the lymph node resection range and the type of gastrectomy as covariates.
- 4) Time taken for gallstone formation

The period from the date of gastrectomy to the date of gallstone formation is calculated based on the following criteria.

Early termination due to gallstone formation within 12 months after gastrectomy or completion due to gallstone formation at 12 months will be treated as an incidence, and the period until the early termination or completion will be computed.

If gallstones are not formed until the completion of the clinical study, it will be treated as cut-off data, and the time to completion will be calculated. If the patient is withdrawn within 12 months after the gastrectomy, it will be treated as cut-off data and the time to dropout will be calculated.

The time taken up to gallstone formation will be presented for each treatment group, and as for the time taken to gallstone formation, comparison between each treatment group of DWJ1319 and the placebo will be analyzed using the cox proportional hazards regression model with the lymph node resection range and gastrectomy as prognostic factors.

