11.2.5. Abdominal Ultrasound

Abdominal ultrasound is performed at Visits 1 (baseline), 3, 4, 5 and 6, or at the time of early termination/withdrawal to determine gallstone formation. At Visits 3 and 6, the abdominal ultrasound should be performed prior to the upper gastrointestinal endoscopy. Also, if abdominal ultrasound is performed on the same day as abdominal CT scan, the abdominal ultrasound should be performed prior to abdominal CT scan. Patients should remain in a fasting state for at least 8 hours before the test up until the end of the test. If the patient is unable to do so, the visit process should stop to reschedule it. If it is difficult to perform abdominal ultrasound on the regular visit due to the testing schedule of each study site, it may be done within regular visit ± 2 weeks.

The investigator confirms through abdominal ultrasound whether gallstones have formed in areas including the liver, gallbladder, and bile ducts. If gallstone formation is confirmed, an ultrasound

Confidential Page 25 of 51

photograph that confirms the formation of gallstones should be stored as an evidence document. Even if gallstone formation is not confirmed, ultrasound photographs that are available for the following four sites should be kept as an evidence document.

- 1) A subcostal scan that allows monitoring both portal veins
- 2) An intercostal scan that allows monitoring the right portal vein
- 3) A subcostal scan that allows monitoring the full length of the gallbladder
- 4) An intercostal scan that allows monitoring the full length of the gallbladder

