13.1. Criteria for Withdrawal from Study

A subject who has signed an informed consent may stop participating in the study at any time during the study period. The reasons for early withdrawal of subjects are as follows:

- 1) Subject's voluntary termination of the study (withdrawal of consent): The investigator confirms that the reason for the withdrawal of consent is not due to adverse events, etc.
- 2) In case of violation of inclusion/exclusion criteria
- 3) If the subject does not visit (failure to follow-up)
- 4) If it is difficult to carry out the study due to adverse events
 : the study may be discontinued at the discretion of the investigator or the subject, regardless of the causal relationship with the investigational product.
- 5) If it is difficult to continue the study at the discretion of the investigator due to the recurrence, etc. of gastric cancer during the study period
- 6) If the study cannot proceed further based on other judgment of the investigator

For subjects who have withdrawn early after randomization, the final evaluation will be conducted according to the schedule for early termination visit regardless of the reason. If they refuse a termination visit or cannot be reached by phone, a call should be made continuously so that all unused investigational products can be returned. The reason(s) for dropout from the clinical study should be recorded in the final assessment section of the case record form.

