6.1.2 Secondary Endpoints

The secondary efficacy endpoints of this study are as follows:

- 1) Percentage of subjects forming gallstones within 3, 6, 9, and 12 months from gastrectomy
- ➤ Percentage of subjects with gallstones formation (%) = (The subjects who were identified as having gallstone formation in at least one of the following sites, gallbladder, bile duct, and intrahepatic bile duct, within 3, 6, 9, and 12 months after gastrectomy/Number of subjects analyzed)*100
- 2) Percentage of subjects forming gallstone within 3, 6, and 9 months from gastrectomy as assessed by the external investigator
- Percentage of subjects with gallstone formation (%) = (Based on external investigator's assessment, the subjects who were identified as having gallstone formation in at least one of the following sites, gallbladder, bile duct, and intrahepatic bile duct, within 3, 6, and 9 months after gastrectomy/Number of subjects analyzed)*100
- 3) Percentage of subjects forming biliary sludge within 3, 6, 9, and 12 months from gastrectomy
- ➤ Percentage of subjects with biliary sludge formation (%) = (The subjects who were identified as having biliary sludge formation at least once within 3, 6, 9, and 12 months after gastrectomy/Number of subjects analyzed)*100
- 4) Time to gallstone formation
- The time to gallstone formation is calculated as the time until the early termination or completion after a gastrectomy, if the gallstone has been formed within 12 months resulting in early termination, or at 12 months resulting in completion. Subjects who do not form gallstones until the completion of the clinical study are treated as censoring and their time period until completion is calculated. If subjects are withdrawn within the 12 months after a gastrectomy, they are treated as censoring data and their time period until the withdrawal is calculated.

^{*} In the case of the subjects who are confirmed to have gallstones by the institutional

Form DA-05-03.03 Statistical Analysis Plan

Sponsor: Daewoong Pharmaceutical Co., Ltd.

Protocol No.: DW_UDCA005 English Translation Version

reviewer and are terminated early from the clinical study, to be conservative, they are defined as subjects with gallstone formation regardless of the external investigator's assessment.

- Time to Gallstone Formation
 - Status = 1, if gallstones were formed
 - = 0 (censoring), if gallstones were not formed until last f/u

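### Time to gallstone is censored at an undefined dropout date rather than at the last scan, so a subject lost after a missed scan can count as stone-free without having been examined

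*Protocol*

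**What the plan says.** Protocol section 14.4.2, item 4, sets three dates for the time-to-gallstone endpoint, all counted from gastrectomy.

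- Subjects who withdraw in the first 12 months: "it will be treated as cut-off data and the time to dropout will be calculated".
- Stone-free completers are censored at the date of completion.
- Subjects with a stone: "the period until the early termination or completion will be computed".

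The date of the scan appears in none of them. SAP section 6.1.2 says the same of withdrawals ("they are treated as censoring data and their time period until the withdrawal is calculated"), and its duration formula uses the completion, early termination or dropout date. The comparison with placebo is a Cox model.

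Stones are looked for at fixed times. Section 11.2.5: "Abdominal ultrasound is performed at Visits 1 (baseline), 3, 4, 5 and 6, or at the time of early termination/withdrawal to determine gallstone formation". Visits 3 to 6 are Months 3, 6, 9 and 12. CT is added at Months 6 and 12.

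Section 13.1 lists non-attendance among the reasons for withdrawal ("If the subject does not visit (failure to follow-up"). It requires that for anyone withdrawn after randomization "the final evaluation will be conducted according to the schedule for early termination visit regardless of the reason". It also foresees subjects who refuse that visit or cannot be reached; the stated aim of the continued calls is then the return of unused product, not a scan.

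**The concern.** A gallstone becomes an event only when imaging shows it. Time after a subject's last scan therefore carries no information on stone status, and a rule that credits it as stone-free time adds people to later risk sets who could not have contributed an event there.

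Take a subject scanned at Month 3 who misses Month 6, attends no termination visit and is recorded as a dropout at Month 7. Under the rule as written, this subject is in the Month 6 risk set as a non-event, although nobody looked.

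Two things are at stake. The incidence implied by the time-to-event data is understated in any arm with such losses. If the losses differ between arms, the hazard ratio is also biased in favour of the arm that loses more.

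**Working it through.** **The plan's own figures.** The documents give no figure for this endpoint, so the event rates and the loss come from the sample size section (protocol 8.3).

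- Placebo: (18 + 112 + 6)/(56 + 661 + 44) = 136/761 = 17.9%, used as 18%.
- Drug: (7 + 1 + 4)/(53 + 61 + 63) = 12/177 = 6.8%, used as 7%.
- Size: (1.96 + 0.842)² × (0.07 × 0.93 + 0.18 × 0.82)/0.11² = 138.01, stated as 138. With 20% loss, 138/0.8 = 172.5, so 173 per group.

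The stated sample size is reproduced and is not in question here.

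**Assumptions that the documents do not give.** The risk per scan is constant. Losses are split equally after the Month 3, 6 and 9 scans, because subjects with no post-randomization gallstone assessment are outside the full analysis set (14.1.1). A share s of the losses has a dropout date after the next, missed scan; s runs from 0.25 to 1.

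**Risk per scan.** Placebo: 1 − 0.82^(1/4) = 0.0484. Drug: 1 − 0.93^(1/4) = 0.0180. Their ratio is 0.371.

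**Expected counts at 20% loss, s = 1.** Losses after each of the three scans: 173 × 0.20/3 = 11.53. Those examined at Month 6 on placebo: 173 − 8.374 − 11.53 = 153.09. The dropout-date rule adds the 11.53 back to the risk set.

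| Scan (month) | Placebo examined | Placebo events | Placebo risk set under the rule | Drug examined | Drug events | Drug risk set under the rule |
|---|---|---|---|---|---|---|
| 3 | 173.00 | 8.374 | 173.00 | 173.00 | 3.110 | 173.00 |
| 6 | 153.09 | 7.410 | 164.63 | 158.36 | 2.847 | 169.89 |
| 9 | 134.15 | 6.493 | 145.68 | 143.98 | 2.589 | 155.51 |
| 12 | 116.12 | 5.621 | 127.66 | 129.85 | 2.335 | 141.39 |

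Cumulative incidence is 1 minus the product of (1 − events/risk set).

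- Censoring at the last scan returns 18.0% and 7.0%.
- Under the rule, placebo is 1 − (1 − 8.374/173.00)(1 − 7.410/164.63)(1 − 6.493/145.68)(1 − 5.621/127.66) = 17.0%. Drug is 6.6%.
- With s = 0.25 the figures are 17.7% and 6.9%.

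**Ratio.** As a stand-in for the Cox hazard ratio, take the Mantel-Haenszel ratio over the four scans, with n the risk sets and e the events: Σ e_T n_P/(n_P + n_T) divided by Σ e_P n_T/(n_P + n_T).

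| Loss, placebo / drug | Last-scan censoring | Dropout date, s = 0.25 | Dropout date, s = 1 |
|---|---|---|---|
| 20% / 20% | 0.371 | 0.372 | 0.373 |
| 10% / 30% | 0.371 | 0.366 | 0.350 |
| 30% / 10% | 0.371 | 0.378 | 0.397 |

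**The case against.** Much of the case on the other side stands.

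- **Every withdrawal is meant to have a final evaluation.** For anyone scanned at that visit, dropout date and last scan coincide and the rule does no harm. The 20% allowance also covers withdrawn consent, adverse events and recurrence, for which that visit is required too. Only those who miss a scan, never attend and are dated after the missed scan are affected. Section 13.1 foresees such subjects, but they are a subset of the withdrawals.
- **The dropout date is undefined.** If it meant the last attended scan visit, the problem would disappear. The SAP's status line, which refers to the last follow-up, is compatible with that, but its duration formula uses the dropout date. Neither document settles it.
- **s = 1 at 20% is an upper-end case under one missed scan.** If some of the 20% leave before Month 3, and so outside the full analysis set, less remains: with 15% lost in the three later intervals, placebo reads 17.3% at s = 1.
- **Little that is reported moves.** The plan gives a Cox comparison and, in the SAP, a median, which would not be reached at 18% incidence.

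A reader might also infer three stronger things that the documents do not support.

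- **That event times are equally wrong.** Section 13.2 ends participation when ultrasound confirms the stone, so the termination date is tied to that scan.
- **That the scan waiver in section 11.3.7 creates the same error.** It requires an ultrasound within the previous 3 months, and scans are 3 months apart, so such a subject will normally not have passed a scheduled scan unexamined.
- **That the rule favours the drug.** It favours whichever arm loses more, and the documents give no reason to expect either.

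**Conclusion.** The point holds in a limited form. As written, the rule counts stone-free time beyond the last examination for subjects lost after a missed scan, and the undefined dropout date leaves open how many subjects that is.

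Under the stated assumptions, the implied incidence is understated by 0.3 to 1.0 percentage point on placebo (18% to between 17.7% and 17.0%) and by 0.1 to 0.4 point on drug (7% to between 6.9% and 6.6%). With balanced loss the hazard ratio is essentially unchanged. A shift to about 0.35 or 0.40 needs both a 30% versus 10% imbalance and every loss affected.

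This is one secondary endpoint. The primary logistic analysis and the by-visit proportions do not use the rule, so no conclusion about the main result follows. It should be corrected because differential loss cannot be ruled out in advance and the correction is cheap.

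**What to change.** In protocol 14.4.2 item 4 and SAP 6.1.2, including the duration formula, censor every subject without a stone at the date of the last evaluable gallstone imaging: ultrasound, or CT where only CT is available. The same wording covers a completer with no Month 12 scan and removes the need to interpret the dropout date.

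For consistency, date the event at the imaging that first showed the stone. This part is minor, given section 13.2.

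The cost is a change of about two sentences in each document. It uses the dates of examinations that the trial already performs and adds no visits. The downside is slightly less nominal follow-up time. The change should be made before unblinding.

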14.4.3. Other Efficacy Endpoints

1) Changes in the bile reflux symptoms from baseline value (score for each area and the overall score) at 3, 6, 9, and 12 months

For scores of questionnaire on bile reflux symptoms, the score of each typical symptom (upper abdominal pain, heartburn, nausea) and the total score of symptoms will be presented in three categories which are frequency, intensity, and the level of distress.

Descriptive statistics (mean, standard deviation, minimum, median, and maximum) for changes in the bile reflux symptom score and changes compared to the baseline value at each time point are provided for each treatment group. And the difference in the changes in the bile reflux symptom score between each treatment group of DWJ1319 and the placebo is analyzed using the analysis of covariance with the lymph node resection range and the type of gastrectomy as covariates.

 Percentage of subjects who developed biliary reflux according to the upper gastrointestinal endoscopy at 3 and 12 months

The frequency and proportion of subjects with biliary reflux at each time point and the corresponding 95% confidence interval are provided for each treatment group. And the difference in the biliary reflux onset rate between each treatment group of DWJ1319 and the placebo is analyzed using a logistic regression model with the lymph node resection range and the type of gastrectomy as covariates.

Percentage of subjects with significant AST and ALT abnormalities at 6 and 12 months
 The frequency and percentage of subjects for whom the AST and ALT of the laboratory test were

Confidential Page 35 of 51

determined to be clinically significant abnormalities at the 6th and 12th month after gastrectomy were presented, and the difference between each dose of DWJ1319 versus placebo for the clinically significant abnormal percentage are analyzed using a logistic regression model with the lymph node resection range and type of gastrectomy as covariates.

14.5. Safety Analysis

Safety analysis is performed for the safety analysis set. Safety endpoints are adverse events, laboratory tests, vital signs, and physical examinations. The baseline for each safety endpoint should use the results of the last assessment performed prior to the first dose of the investigational product.

14.5.1. Adverse Events

Summary and analysis of adverse events are performed on treatment-emergent adverse events (TEAE). Adverse events following treatment are those that did not occur before the treatment, but the adverse events that occurred after the treatment or adverse events that became worse even if they are symptoms that existed prior to the treatment.

Descriptive statistics (number of subjects, incidence, and number of cases) will be presented by treatment group for the treatment emergent adverse event (TEAE), adverse drug reaction (ADR), and serious adverse event (SAE), and the two-sided 95% confidence interval for the incidence will also be presented. The differences in proportions between the treatment groups will be compared using the chi-square test or Fisher's exact test. All adverse events (TEAE) that occurred after the drug administration, adverse drug reactions (ADR) and serious adverse events (SAE) should be coded according to System Organ Class (SOC) and Preferred Term (PT) using MedDRA. The number of subjects who have manifested coded adverse events, incidence, number of cases, etc. should be presented for each treatment group. The relevance with the investigational product and severity will be assessed and presented by categorizing by SOC. In addition, a detailed report should be written about SAEs.

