5.1. Study Objective

- To assess the efficacy of DWJ1319 300 mg or DWJ1319 600 mg administered once daily for 52 weeks in the prevention of gallstone formation after gastrectomy in patients with gastric cancer compared with placebo.
- 2) To assess the safety and tolerability of DWJ1319 300 mg or DWJ1319 600 mg administered once daily for 52 weeks compared with placebo.

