6.4. Justification for Setting Dose of Study Drug

This study will be performed in three groups of placebo, 300 mg or 600 mg DWJ1319 to verify the

Confidential Page 16 of 51

preventive effect of DWJ1319 for gallstone in patients with gastric cancer who underwent gastrectomy.

The preventive effect of UDCA for gallstone was confirmed in clinical studies in patients who experienced rapid weight loss, and an optimal dose was assessed as 600 mg/day. At this time, no significant difference was observed between the two treatment groups of 600 and 1200 mg. ¹⁹⁾

Assessment of the gallbladder dissolution effect of UDCA in gallbladder patients by dose also showed that the gallbladder dissolution effect of UDCA was the highest at 500 mg. The gallbladder dissolution rate between the two treatment groups, 500 and 1000 mg/day, was not significantly different.²⁴⁾

Because UDCA's gallstone prevention and treatment mechanism are related to its function as a tertiary bile acid and it is anticipated that the gallstone prevention mechanism will work the same even if the patient group is different, the optimal dose of UDCA for patients with gastric cancer is also expected to be 600 mg/day. However, since no study has confirmed the preventive effect of UDCA for gallstones in patients with gastric cancer who underwent gastrectomy, the objective is to verify the gallstone prevention effect in two treatment groups of DWJ1319 300 mg and 600 mg and to verify the optimal dose.

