14.5.2. Laboratory Tests and Vital Signs

Descriptive statistics (mean, standard deviation, minimum, median, and maximum) will be presented by treatment group for the measurements at each time point and the change from baseline after the administration of the investigational product, and the frequency and proportion will be presented for categorical measurement results.

The treatment groups will be compared by ANOVA or a Kruskal–Wallis test for continuous data, and by the chi-square test or Fisher's exact test for categorical data.

For laboratory tests, classification should be made into a normal or not clinically significant abnormality and clinically significant abnormality. A shift table will be presented for changes in the post-administration compared to pre-administration of the investigational product. The chi-square test or the Fisher's exact test will be used to analyze the proportion of patients who have changed to clinically significant abnormalities post-dose at a not clinically significant abnormality.

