9.2.1 Overall Summary of Adverse Events

The number of subjects, expression rate (%) and the number occurrences of TEAEs and ADRs during the clinical study are presented as well as the 95% confidence intervals for the expression rate. However, a 95% accurate confidence interval for expression rate is presented when a cell with an expected frequency of less than 5 is equal to 20% or higher of all cells. The chi-square test or Fisher's exact test is used to determine whether there is a significant difference among the treatment groups, and the severity of the collected adverse events and their relevance to the investigational product are presented.

Also, serious adverse events, adverse events that resulted in permanent discontinuation of investigational product treatment, and adverse events that resulted in death are summarized.

A summary of the data is presented in the following tables.

- T. Overall Summary of TEAEs (Safety Set)
- T. Overall Summary of ADRs (Safety Set)

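### The safety objective compares each dose with placebo, but the safety section plans only three-group tests and no dose-minus-placebo estimate (minor)

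*Protocol*

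**What the plan says.** Protocol 5.1 gives the second objective as "To assess the safety and tolerability of DWJ1319 300 mg or DWJ1319 600 mg administered once daily for 52 weeks compared with placebo". Section 6.4 confirms the arms: "This study will be performed in three groups of placebo, 300 mg or 600 mg DWJ1319".

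The safety section plans the following.

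- **14.5.1, adverse events.** Counts and incidence by arm for TEAEs, ADRs and SAEs, with a two-sided 95% confidence interval for each arm's incidence. Then: "The differences in proportions between the treatment groups will be compared using the chi-square test or Fisher's exact test". Events coded by SOC and PT are tabulated by arm.
- **14.5.2, laboratory tests and vital signs.** "The treatment groups will be compared by ANOVA or a Kruskal–Wallis test for continuous data", and chi-square or Fisher for categorical data. The proportion shifting to clinically significant abnormality is also tested by chi-square or Fisher.

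Neither subsection names a contrast of one dose with placebo, a difference, or an interval for a difference.

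The efficacy sections are worded differently. Sections 14.4.2 and 14.4.3 compare each DWJ1319 group with placebo. This includes a laboratory measure, clinically significant AST/ALT abnormality, where "the difference between each dose of DWJ1319 versus placebo for the clinically significant abnormal percentage are analyzed using a logistic regression model".

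The SAP keeps the three-group wording for adverse events. Its section 9.2.1 says the chi-square or Fisher test "is used to determine whether there is a significant difference among the treatment groups".

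**The concern.** The objective contains two questions: does 300 mg differ from placebo, and does 600 mg differ from placebo? A three-group test has one null hypothesis, that all three arms are equal. It can reject because of 600 mg alone, because of 300 mg alone, or because the doses differ from each other while neither is clearly different from placebo. Its p-value does not separate these cases.

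Dose-specific safety matters here because 6.4 says the trial studies two doses in order to verify the optimal one. A reader of the safety tables would have a global p-value and three separate arm-level intervals. There would be no estimate of the excess risk of either dose over placebo and no statement of how large an excess the data leave open.

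**Working it through.** **1. Is the planned test a three-group test?** ANOVA and Kruskal–Wallis on three arms, with no contrast named, test equality of all arms. For laboratory values and vital signs this is certain. For chi-square and Fisher it is the natural reading: the groups are named collectively, while the efficacy text names each dose against placebo. SAP 9.2.1 supports this reading, but the point does not depend on it.

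**2. Number per arm.** No figure is stated for the safety comparisons. The only planning figure is the sample size in 8.3, and it reproduces:

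(1.96 + 0.842)² × (0.07×0.93 + 0.18×0.82) / 0.11² = 7.851 × 0.2127 / 0.0121 = 138.0

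Then 138 / 0.8 = 172.5, so 173 per arm and 3 × 173 = 519. The safety set is everyone randomised and dosed (14.1.2), so up to 173 per arm.

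**3. Do the two answers differ?** The overall adverse event rates below are assumptions, as the documents give none for this population. Trials were simulated with binomial counts, 173 per arm, 40,000 runs per row. Each was tested by Pearson chi-square at two-sided 5%: 2 df for three groups, 1 df for each dose against placebo.

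| Placebo/300/600 mg | Three-group test rejects | 600 mg vs placebo | 300 mg vs placebo | Three-group significant, neither dose significant vs placebo |
|---|---|---|---|---|
| 20/25/30% | 47% | 58% | 20% | 1% |
| 20/15/25% | 54% | 20% | 23% | 16% |
| 20/20/30% | 61% | 58% | 5% | 8% |

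In the first row, 600 mg is significantly different from placebo while the three-group test is not significant in 13% of trials. In the third row the three-group test is slightly more sensitive than the direct test. So the issue is which question is answered, not a general loss of power.

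**4. Two worked tables (events out of 173: placebo, 300 mg, 600 mg).** With equal arms, chi-square = Σ(x − E)² / [E(1 − p)], where E is the mean count and p the pooled rate.

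*35, 43, 51.*
- Three groups: E = 43, p = 129/519 = 0.2486. Chi-square = (64 + 0 + 64) / (43 × 0.7514) = 3.96 on 2 df, p = 0.138.
- 600 mg vs placebo: E = 43, p = 86/346 = 0.2486. Chi-square is again 3.96, but on 1 df, p = 0.047.
- 300 mg vs placebo: E = 39, p = 78/346 = 0.2254. Chi-square = 32 / (39 × 0.7746) = 1.06, p = 0.303.

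*35, 26, 45.*
- Three groups: E = 35.33, p = 106/519 = 0.2042. Chi-square = (0.11 + 87.11 + 93.44) / (35.33 × 0.7958) = 6.43 on 2 df, p = 0.040.
- 600 mg vs placebo: E = 40, p = 80/346 = 0.2312. Chi-square = 50 / (40 × 0.7688) = 1.63, p = 0.202.
- 300 mg vs placebo: E = 30.5, p = 61/346 = 0.1763. Chi-square = 40.5 / (30.5 × 0.8237) = 1.61, p = 0.204.

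The first table hides a 600 mg difference behind a non-significant global test. The second is globally significant because the doses differ from each other.

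**5. What the missing estimate would show.** For the first table, 600 mg minus placebo = 16/173 = 9.2 points. Standard error = √[(0.2023×0.7977 + 0.2948×0.7052)/173] = 0.0462, so the 95% interval is 9.2 ± 9.1, about 0.2 to 18.3 points. For 300 mg minus placebo, 8/173 = 4.6 points with standard error 0.0449, giving about −4.2 to 13.4 points. The second interval shows what a p-value of 0.303 leaves open.

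**The case against.** Several points on the other side are sound and limit the concern.

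- **Comparative information exists.** Arm-level incidences with 95% confidence intervals, SOC/PT and severity tables, shift tables and SAE reports are all planned. Clinically significant AST/ALT abnormality is compared per dose in 14.4.3; SAP 8.4.3 adds odds ratios with intervals. A reader might infer that the global p-value is the only comparative safety result, but these outputs show otherwise. What they lack is an excess over placebo with an interval for adverse events, vital signs and the other laboratory parameters.
- **Rejection when only 600 mg is raised is correct.** The three-group null is then false. A reader might call this a false alarm about 300 mg, but the arm-level incidences would help show which arm is raised.
- **No test is planned for single event terms.** In 14.5.1 the test follows overall TEAE, ADR and SAE incidence; coded terms are only tabulated. It is tempting to take individual events from Appendix 3 and compute how often the test would flag or miss them. The documents do not attach the test to such terms.
- **No wrong inference is written down.** The protocol nowhere equates a non-significant test with comparable safety. A non-significant pairwise test would not clear a dose either, and failure to detect modest harms is mainly a matter of sample size.
- **Detail may belong in the SAP.** The choice of interval method does. The test itself, however, is stated in the protocol, and it does not match the stated objective.

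**Conclusion.** The mismatch is real and minor. The objective is each dose against placebo. The safety section states tests across three groups and plans no dose-minus-placebo estimate. The three-group reading is certain for ANOVA/Kruskal–Wallis and the natural one for chi-square/Fisher.

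Under the assumed overall rates and 173 per arm, the two questions diverge in both directions: 47% against 58% rejection for a graded increase, and 16% of trials globally significant with neither dose different from placebo when the doses lie on either side of it. These sizes depend on the assumed rates.

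The documents do not support the stronger claim that the safety analysis as a whole cannot inform on either dose. That limit applies to the global p-value alone. Safety is not a confirmatory endpoint, so the primary conclusion and the sample size are unaffected.

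**What to change.** In protocol 14.5.1 and 14.5.2, with matching text in the synopsis and the SAP safety sections, add two comparisons: 600 mg minus placebo and 300 mg minus placebo.

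- For overall TEAE, ADR and SAE incidence and for shift to clinically significant abnormality: risk difference with 95% confidence interval.
- For laboratory and vital-sign changes from baseline: difference in mean change with 95% confidence interval.
- Any three-group p-value may stay, labelled descriptive.

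The interval method can be left to the SAP. The cost is wording and two extra columns in existing tables, with no new data or patients. The drawback is two dose comparisons for each measure, all descriptive and unadjusted for multiplicity, which the text should state.
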